# 4.4. End of Study Definition

A subject is considered to have completed the study if he/she has completed all phases of the study including the last scheduled procedure shown in the Schedule of Assessments (SoA) (Table 2). The EOS is defined as the date of the last visit of the last subject in the study.

### 5. STUDY POPULATION

### 5.1. Inclusion Criteria

Subjects are eligible to be included in the study only if all of the following criteria apply:

- 1. Subject understands the study design and has been informed of the investigational nature of the study. Subject has given voluntary, written, informed consent to take part in this study.
- 2. Subject agrees to be compliant and is capable of completing the required study assessments.
- 3. Male or female age  $\ge 21$  to  $\le 75$  years at time of signing informed consent.
- 4. All subjects (male or female) who are of childbearing potential must agree to use highly-effective, double contraception (with male/female partners) during the study. Double contraception is defined as use of a condom by the male partner, combined with use of 1 of the following forms of highly-effective contraception by the female partner:
  - a. Oral contraceptive pills
  - b. Depot or injectable contraceptive
  - c. Intrauterine device (IUD)
  - d. Contraceptive patch (e.g., Xulane®) or NuvaRing®
  - e. Documented evidence of tubal ligation at least 6 months prior to the screening visit).

Male subjects with a history of vasectomy should also use condoms as double contraception during the study. Use of highly-effective, double contraception must continue for 30 days or 5 half-lives (whichever is longer) after the last dose of IP. Female subjects must not donate oocytes during this time. Male subjects must not donate sperm during this time. Rhythm methods are not considered as highly-effective methods of birth control. Subject abstinence for the duration of the study and 30 days or 5 half-lives (whichever is longer) after last dose of IP is acceptable if it is the subject's regular practice.

- 5. Females of childbearing potential must have a negative serum pregnancy test at screening and agree to undergo a urine pregnancy test at pregnancy test at end of the study . , and a serum pregnancy test at end of the study
- 6. Females not of childbearing potential will be defined for this study as postmenopausal (defined as cessation of regular menstrual periods for at least 12 months) and confirmed by follicle-stimulating hormone (FSH) level OR surgically sterile (e.g., total hysterectomy, partial hysterectomy, or oophorectomy).
- 7. Serum TG criteria meeting all of the following criteria:
  - a. A historical documented TG ≥400 mg/dL (4.52 mmol/L) in the past 5 years from screening or currently on lipid-modifying therapy due to SHTG at screening
  - b. Mean of 2 screening fasting serum TGs ≥500 mg/dL (5.65 mmol/L) and ≤2000 mg/dL (22.60 mmol/L). The target for the study is 500 mg/dL. Due to TG variability, up to 10% of subjects enrolled may have a mean qualifying TG level between 475 and 500 mg/dL. Mean screening fasting serum TG is defined as the mean of TG if the average of TG at is <500 mg/dL, or

- >2000 mg/dL. The repeat measure of TG is permitted at a minimum of 7 days apart at
- c. If 1 of the 2 qualifying TGs is <400 mg/dL, the difference between 2 TG should be <300 mg/dL. Note: If a subject has an individual fasting TG value of <350 mg/dL at any one visit or mean of two fasting TG levels <475 mg/dL, they will be considered a screen fail and not eligible to be re-screened.
- 8. Willing to maintain current eating and exercise habits from time of signing the informed consent and for the duration of the study. (See also Inclusion Criterion #11 and Exclusion Criterion #10 regarding alcohol consumption and Exclusion Criterion #4 regarding weight changes.)
- 9. Concomitant medication may include prescription fish oil (including purified eicosapentaenoic acid [EPA] with or without docosahexaenoic acid [DHA]) and/or statin with or without ezetimibe (none of which will be supplied as part of study) as long as the subject has been clinically stable (per Principal Investigator [PI] judgment) while on stable dose for
- 10. Medicines known to exacerbate hypertriglyceridemia (such as certain beta blockers, thiazides, estrogens, bile acid sequestrants) should be stable

  ) and remain stable during the study.
- 11. Subject is willing to refrain from alcohol consumption for ≥48 hours before each study visit.
- 12. MRI-PDFF of  $\geq$  6.0% for subjects screened for the fibrate expansion cohort. Note: Those who cannot undergo MRI for any reason (e.g., claustrophobia, metal implants) cannot participate in the fibrate expansion cohort.

### 5.2. Exclusion Criteria

Subjects are excluded from the study if any of the following criteria apply:

- 1. Females who are pregnant or breastfeeding, or planning to become pregnant, or breastfeed while enrolled in the study or within 30 days or 5 half-lives (whichever is longer) after last dose of IP.
- 2. Uncontrolled or newly diagnosed (< 3 months since diagnosis at time of Screening) **hypertension**. Subjects with well controlled hypertension who are clinically stable may enroll if they have been on a stable dose of antihypertensive medications for at least 2 months before Screening. Subjects who are taking >2 antihypertensive medications may be eligible with Medical Monitor (or designee) approval.
- 3. Body mass index (BMI) >45 kg/m^2 at screening
- 4. Weight change ≥5% in 3 months prior to screening or weight change ≥5% between screening .
- 5. Central laboratory hemoglobin levels below the lower limit of normal (<12.0 g/dL for males, <11.0 g/dL for females), or dialysis, lipid apheresis, plasma exchange, blood transfusion, or blood donation/blood loss of ≥400 mL at least a month prior to and during

the screening period or anticipation of these procedures during the period of the study and up to 30 days afterwards.

- 6. A history of symptomatic gallstone disease unless treated with cholecystectomy and/or pancreatitis within 5 years from screening will be excluded from the study.
- 7. ALT or AST  $>3 \times$  upper limit of normal (ULN) at screening
- 8. Total bilirubin exceeds ULN at screening  $\blacksquare$ , unless prior diagnosis and documentation of Gilbert's syndrome in which case total bilirubin must be  $\leq 3 \text{ mg/dL}$ .
- 9. Creatine kinase (CK) > 5  $\times$  ULN at screening
- 10. Risky drinking (defined as alcohol intake >14 standard drink units per week or 4 standard drinks on a single occasion in men; and alcohol intake >7 standard drink units per week or 3 standard drinks on a single occasion in women) within the 24 months before screening or had positive alcohol test at screening. A unit of alcohol is defined as 14 gram or as 355 mL of beer (5% alcohol by volume [ABV]), 1 glass of wine (150 mL; 12% ABV), or 1 shot of hard liquor (45 mL; 40% ABV). During the study, subjects will receive counseling and will be encouraged to abstain from alcohol. Alcohol intake will be limited to 2 units of alcohol per day for men and 1 unit of alcohol per day for women. Subjects must be willing to abstain from alcohol use 48 hours prior to study visits.
- 11. Concomitant use of PCSK9 inhibitors, niacin, or any supplements, including non-prescription, non-pharmaceutical strength fish oils, used to alter lipid metabolism. Previous treatment with a PCSK9 inhibitor will need to have ceased >12 weeks before screening with no intention to reinitiate treatment for the duration of the trial. Other lipid-modifying supplements including, but not limited to, red rice yeast supplements, garlic supplements, soy isoflavone supplements, sterol/stanol products, or policosanols are not permitted.
  - a. Subjects participating in the main cohort previously treated with a fibrate will need to agree to cease fibrate treatment for the duration of this trial.
  - b. Subjects enrolled in the fibrate expansion cohort will need to maintain their current stable dose of fibrate therapy (≥4 weeks before screening ...).
- 12. Previous long-term (>4 weeks) use of systemic steroid (glucocorticoid) medications such as prednisone within 12 months of screening. Inhaled or topical corticosteroids are permitted.
- 13. Reduced renal function (eGFR ≤ 55 mL/min/1.73 m² calculated using chronic kidney disease epidemiology collaboration [CKD-EPI] equation).
- 14. Positive for hepatitis B virus (HBV), hepatitis C virus (HCV) or human immunodeficiency virus (HIV). HIV, HBV and HCV determined by antibodies first and, if positive, confirmed by DNA/ribonucleic acid (RNA). Subjects who have tested positive for COVID-19 who are asymptomatic or who have active COVID-19 infection are excluded. Note: subjects who had COVID-19 and recovered without sequelae or tested positive without symptoms at least 8 weeks prior to screening may be included.

89bio Confidential Page 41

- 15. History of substance use disorder, or any other substance dependence (with the exception of caffeine) as defined by the Diagnostic and Statistical Manual of Mental Disorders 4th edition Text Revision (DSM-IV-TR) in the past 2 years prior to Screening. Subjects without a history of substance use disorder who have a positive drug screen test at Screening may be considered for enrollment with Medical Monitor (or designee) approval.
- 16. Participation in a previous clinical trial or exposure to another investigational drug within 12 weeks or 5 half-lives, whichever is longer, prior to screening.
- 17. Previous exposure to an FGF21 analog

  r FGFR1 activating product or known sensitivity to PEG or any of the excipients.
- 18. Type 1 diabetes mellitus (T1DM).
- 19. Diagnosis of Type 2 diabetes mellitus (T2DM) <6 months prior to screening.
- 20. Subjects with T2DM diagnosed ≥ 6 months prior to screening must have a HbA1c < 9.5% and if receiving antidiabetic medications, must be on a stable regimen before screening. A stable regimen is defined as no addition or discontinuation of antidiabetic medications, but dose adjustments or switching to another medication in the same class at the same relative dose per standard of care are allowed. Insulin, dipeptidyl peptidase IV (DPP-IV) antagonists and other oral medications are allowed if subject has been on a stable regimen for at least 3 months. Glucagon-line peptide 1 (GLP-1) agonists and sodium glucose co-transporter 2 (SGLT2) inhibitors are allowed if subject has been on stable doses for 6 months. Use of thiazolidinediones such as pioglitazone, which can reduce serum TGs, are NOT allowed in this study.
- 21. History of malignancy within 5 years prior to screening other than successfully treated basal or squamous cell carcinoma or localized cervical carcinoma.
- 22. Inadequately controlled thyroid disorders. Subjects on thyroid replacement should be on stable doses for at least 2 months prior to screening.
- 23. Subjects with known lipoprotein lipase impairment or deficiency (Fredrickson Type 1), apolipoprotein C-II deficiency, or familial dysbetalipoproteinemia (Fredrickson Type 3).
- 24. Clinically or otherwise documented cardiovascular or cerebrovascular disease including clinically significant anomalies of rhythm or pattern of ECG or New York Heart Association Class II to IV heart failure within 12 months of screening that, in the judgment of the Investigator, could affect the safety of the subject or their ability to comply with the study requirements.
- 25. History of bone trauma, fracture, or surgery within 2 months of screening or other bone disorders, such as osteoporosis, osteomalacia, and known untreated severe vitamin D deficiency (serum 25-hydroxy-vitamin D ≤5 ng/mL).
- 26. Subject who cannot fast for study procedures for any reason per Investigator's assessment will be excluded. Subjects with T2DM who are treated by insulin secretagogues will need to consult their treating physician about the optimal timing to take these medications to enable them to fast safely for study procedures.

- 27. An employee of the investigational center or has a family member who is involved with the conduct of this study.
- 28. Any other condition(s) that would compromise the safety of the subject or compromise the quality of the clinical study, as judged by the Investigator.

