### **Overall Design**

Study BIO89-100-221 is a randomized, double-blind, placebo-controlled, Phase 2 study to evaluate the efficacy, safety, tolerability, PK and PD profiles, and of BIO89-100 administered SC for 8 weeks. The main cohort will include ~90 subjects with SHTG without concurrent fibrate therapy and will consist of 5 treatment groups to compare 4 dose levels/regimens of BIO89-100 versus placebo. The fibrate expansion cohort will include ~36 subjects with SHTG on stable background fibrate therapy and with a baseline MRI-PDFF ≥ 6.0% and will consist of 2 treatment groups comparing one dose regimen of BIO89-100 versus placebo. Investigators whose sites are obtaining MRIs should assess if subjects on background fibrate therapy are appropriate for the main cohort (acceptable to washout fibrate therapy) or for the fibrate expansion cohort. For participation in the fibrate expansion cohort, investigators should first discuss the potential subject with the Medical Monitor.

The study includes lifestyle stabilization, TG qualification, treatment, and follow-up periods.

After signing the informed consent form and confirmation of general eligibility, subjects will undergo further screening assessments to confirm eligibility over a period of ~6 to 9 weeks. Generally, eligible subjects will enter a 4- or 6-week lifestyle stabilization period (maximum of 6 weeks for subjects stopping lipid-altering therapy, minimum of 4 weeks for subjects already on stable, protocol-accepted lipid-altering therapy), followed by a ~2-week TG qualification period with qualifying TG measurements

If mean TG levels are not within the inclusion range, an additional week will be allowed for an additional measurement

Individuals who do not meet the criteria for participation in this study (screen failures other than for TGs) may be re-screened, at least 7 days later, if the reason for screen failure is deemed temporary and is resolved prior to re-screening (e.g., respiratory infection). Re-screened subjects will sign a new consent and be assigned a new ID. Subjects can only re-screen once. Re-screening subjects who have maintained the lifestyle stabilization period may be allowed to forgo repeated tests at the discretion of the Medical Monitor. Re-screening after COVID-19 infection requires Medical Monitor approval.

[figure not shown]

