Current approved therapies for SHTG, as an adjunct to diet, include multiple fibrates (approved by the FDA from 1993 to 2009), niacin (extended release approved by the FDA in 1997), and omega-3 fatty acids (approved in 2004, 2012, and 2014). Fibrates, niacin, and prescription omega-3 fatty acids, alone or in combination, can reduce TG by 20% to 50% in some patients with moderate to severe hypertriglyceridemia. However, minimal effects are seen in other patients, especially those with mutations in genes in the lipoprotein lipase pathway (Brisson, et al 2010). Statins have a modest TG lowering effect and are used in patients with moderately elevated TG levels, but they should not be used alone in patients with severe or very severe hypertriglyceridemia.

In patients at high risk for pancreatitis, fibrates remain first line drug treatment, but LDL-C levels may increase during therapy with fibrates which is a detrimental effect in this patient population. Fibrates are associated with an increase in the incidence of cholesterol gallstones, increases in transaminases and creatinine, among other safety and tolerability concerns (Lopid US Package Insert, 2017; Tricor US Package Insert, 2018). Further, due to increased risk of myopathy, the combination of gemfibrozil and statins should be avoided (Berglund, et al. 2014).

The approvals of the omega-3-acids (namely Vascepa® and Epanova®) represent advances in the therapeutic options with improved risk:benefit profiles as compared to the fibrates and niacin formulations. While currently approved therapies are proven to reduce TG levels, the treatment goal of alleviating SHTG, i.e., reducing TG levels to below 500 mg/dL remains a significant challenge. In the Phase 3 studies with Vascepa® and Epanova®, ~50% of the subjects did not have TG level reduction below 500 mg/dL at the end of the 12-week studies (Chowdhury, 2012; Chowdhury, 2014). Patients with TG levels above 500 mg/dL remain at risk for AP as well as cardiovascular and fatty liver diseases. There remains a critical need for new therapies that will reliably reduce TG levels below 500 mg/dL rapidly after diagnosis.

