## 6.7. Concomitant Therapy

Any medication or vaccine (including over-the-counter or prescription medicines, vitamins, and/or herbal supplements) or other specific categories of interest that the subject has received within 3 months from Screening (prior therapy), is receiving at the time of enrollment, or receives during the study must be recorded along with:

- Reason for use
- Dates of administration including start and end dates
- Dosage information including dose and frequency

The Medical Monitor should be contacted if there are any questions regarding concomitant or prior therapy.

Concomitant medication may include prescription fish oil (including purified EPA with or without DHA) and/or statin with or without ezetimibe (none of which will be supplied as part of study) as long as the subject has been clinically stable (per PI judgment) while on stable dose for ≥4 weeks before screening and will maintain stable dose during the duration of the study.

Elevated levels of FGF21 have been linked to reduced cytochrome P450 3A (CYP3A) mRNA expression and activity in NAFLD patients (Woolsey et al, 2016). The underlying mechanism has not been fully elucidated and whether such effects will be observed in SHTG patients is unknown. However, subjects receiving concomitant administration of CYP3A4 substrates with narrow therapeutic index should be closely monitored for any potentially related safety events, and dose adjustment of the CYP3A4 substrate should be considered as needed.

COVID-19 vaccine, if available, will be allowed but subjects are prohibited from participation in interventional COVID-19 vaccine clinical trials.

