#### 6.7.1. Prohibited Medications/Therapies

Subjects must abstain from taking lipid-modifying supplements after the start of screening until completion of the EOS visit, unless, in the opinion of the Investigator and the Medical Monitor, the medication is required.

Other prohibited therapies include:

- Use of PCSK9 inhibitors, niacin, or any supplements, including non-prescription, non-pharmaceutical strength fish oils, used to alter lipid metabolism. For subjects enrolled in the main cohort, use of fibrates is prohibited.
- Medicines known to exacerbate hypertriglyceridemia (such as certain beta blockers, thiazides, estrogens, bile acid sequestrants) should be stable (≥4 weeks before screening and remain stable during the study.
- Other lipid-modifying supplements including, but not limited to, red rice yeast supplements, garlic supplements, soy isoflavone supplements, sterol/stanol products, or policosanols.
- Long-term (>4 weeks) use of systemic steroid (glucocorticoid) medications such as prednisone. Inhaled and topical steroids are acceptable.
- Use of thiazolidinediones such as pioglitazone
- Any IP, FGF21 analog or FGFR1 activating product.

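### The fibrate expansion cohort can enrol subjects taking gemfibrozil with a statin, a pair the protocol's own background section says to avoid

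*Protocol*

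**What the plan says.** Protocol section 2.2.1, which is background, states that "due to increased risk of myopathy, the combination of gemfibrozil and statins should be avoided". It also says that "In patients at high risk for pancreatitis, fibrates remain first line drug treatment".

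The rules that govern enrolment and treatment are these:

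- **Statins.** The study rationale (section 2.1) opens the trial to statin users in both cohorts. Inclusion 9 and section 6.7 permit a statin "as long as the subject has been clinically stable (per PI judgment) while on stable dose" (at least 4 weeks before screening, per section 6.7) "and will maintain stable dose during the duration of the study". Neither places a condition on which fibrate is taken.
- **Fibrates, expansion cohort.** Exclusion 11b: "Subjects enrolled in the fibrate expansion cohort will need to maintain their current stable dose of fibrate therapy". No agent is named or excluded.
- **Fibrates, main cohort.** Section 6.7.1: "For subjects enrolled in the main cohort, use of fibrates is prohibited". The list has no matching entry for gemfibrozil, alone or with a statin, in the expansion cohort.
- **Entry review.** For the expansion cohort, "investigators should first discuss the potential subject with the Medical Monitor" (Overall Design). Exclusion 28 lets the investigator exclude for "Any other condition(s) that would compromise the safety of the subject".
- **CK.** Exclusion 9 removes subjects with CK above 5 × ULN at screening, and CK is part of the scheduled chemistry panel.

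**The concern.** The protocol identifies a specific drug interaction and its hazard, then opens a cohort defined by continued fibrate use without addressing that interaction in its eligibility or prohibited-medication rules. Because statins are also permitted, the two permissions together admit the pair, and the stable-dose conditions on each drug expect it to continue through the study.

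What is at stake is the risk of muscle injury in any such subject. An investigator may still change either drug for safety. But the written rules leave to individual judgement something a single clause would settle. The protocol does name other agents outright, including thiazolidinediones, niacin, PCSK9 inhibitors and red rice yeast, so naming drugs is its normal practice. Section 8 also disallows waivers, so the written criteria are the operative control.

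**Working it through.** There is no planned figure to reproduce. The check is whether a subject stable on gemfibrozil plus a statin is stopped by any readable rule, and what the existing safeguards do.

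**1. Walk the subject through the medication rules.**

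| Rule | Result for gemfibrozil + statin |
|---|---|
| Inclusion 9 and section 6.7 (statin) | Allowed if the dose is stable and the investigator judges the subject clinically stable |
| Exclusion 11b (fibrate) | Allowed; current dose to be maintained |
| Section 6.7.1 (prohibited drugs) | Fibrate ban does not apply to this cohort; the pair is not listed |

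Apart from the section 2.2.1 warning and the package-insert citations, gemfibrozil is not mentioned in the readable text of either document. The subject passes.

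**2. Sort the safeguards.**

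- *Discretionary:* the investigator's clinical-stability judgement on the statin, the Medical Monitor discussion before entry, contact with the Medical Monitor over concomitant-therapy questions, and exclusion 28. None names the combination, and a subject tolerating both drugs would ordinarily be called stable.
- *Reactive:* the CK exclusion at screening, CK in the chemistry panels, follow-up of clinically significant laboratory values (section 8.2.4), the instruction in section 8 to raise immediate safety concerns with the Medical Monitor, and withdrawal by the investigator (section 7.3). The CK exclusion is mandatory, but it acts only once CK is already raised.
- *Fixed but not aimed at the pair:* the eGFR exclusion (≤ 55 mL/min/1.73 m²) and the liver discontinuation rules in section 6.8.1. The readable text has no CK or myopathy stopping rule.

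**3. Count the CK monitoring.** In Protocol Table 2 the chemistry row has 13 visit columns and is marked in columns 1, 3, 4, 8, 12 and 13, which is 6 panels. The dosing row is marked in columns 4 to 11, so column 4 is the first-dose visit. The panels after the first dose are columns 8 (mid-treatment), 12 (end of treatment) and 13 (follow-up), which is 3. These detect muscle injury; they do not prevent it.

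**4. Bound the number affected.** Neither document says how many fibrate users take gemfibrozil or how many of those take a statin. The range is therefore 0 to the planned 36 (18 per arm). SAP section 5.5 says that few subjects enrolled in this cohort, so the real ceiling is probably lower.

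**5. Check the alternative of fibrate washout into the main cohort.** Allocation there is 1:1:1:1:1, so the chance of placebo is 1/5 = 20% for 8 weeks, in subjects whose qualifying triglycerides are about 500 to 2000 mg/dL. Washout is thus not a free way out for these subjects.

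**The case against.** The strongest case against runs as follows. Section 2.2.1 is general prescribing background, not a trial rule, so no two rules conflict. The trial neither starts nor supplies either drug. A gate specific to this cohort, the Medical Monitor discussion, already exists; section 6.7 requires all concomitant drugs to be recorded; and the CK exclusion is compulsory and applied before any study dose. Excluding such a subject leaves the regimen unchanged outside the trial and removes the scheduled CK checks. A flat ban could also prompt someone to stop a statin or switch fibrate in order to qualify, in a population at raised cardiovascular risk, and would narrow a cohort that already recruited poorly. Finally, text is redacted: inclusion 9 and exclusion 11b are cut short, and little of the risk assessment in section 2.3.1 can be read, so guidance may exist there.

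Much of this stands as a limit on severity. The point is a hazard not carried into the rules, not a contradiction between rules, and no added harm caused by enrolment can be shown. The risk of a switch or a stopped statin is a genuine cost of a ban. The redactions leave some doubt, although section 6.7 gives the statin permission in full and section 6.7.1, where one would expect a ban, is largely readable; neither mentions gemfibrozil.

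It does not remove the point. The entry discussion has no stated criterion on this pair, CK rules act after enzymes rise, and the protocol as written expects continued dosing of both drugs that its own background says should not be combined.

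**Conclusion.** The concern holds, at low severity. On the readable text, a subject taking gemfibrozil and a statin can enter the fibrate expansion cohort and is expected to keep both doses stable. No readable safeguard addresses the combination itself. The number affected lies between 0 and 36 and may be zero. It is a patient-safety matter only.

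The conclusion assumes that the redacted parts of inclusion 9, exclusion 11b and section 2.3.1 contain no bar on the pair. It rests on the protocol's own statement of the myopathy risk, with no outside estimate of its size.

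**What to change.** Add one sentence to exclusion 11b and to section 6.7.1: *Concomitant gemfibrozil and statin use is not permitted in the fibrate expansion cohort.* Have the existing Medical Monitor discussion confirm the fibrate's name and any statin use before randomisation.

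Do not direct affected subjects to fibrate washout. Leave that to the case-by-case assessment already described under Overall Design, noting the pancreatitis risk of stopping a fibrate. For the same reason, state that a statin should not be stopped merely to qualify.

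The cost is one clause in two places and one item in a discussion already required, using medication data that section 6.7 already collects. It may slightly reduce the eligible pool in a cohort with low enrolment. If enrolment has closed, carry the clause into the Phase 3 programme that section 4.2 says this study will inform.
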